4.4.1.2 Aqueous Humor Biomarker assessment

The AH sample is collected at Baseline and at the week 16 visit.

The number of patients with sample collection will be summarized at Baseline and week 16.

The analysis of changes from baseline in AH biomarker patterns over time will be reported in a separate document as per section 4.4.

4.4.2 Sensitivity Analyses

Not Applicable.

4.4.3 Subgroup Analyses

The exploratory endpoints will be summarized by the following subgroups, provided that they include at least 30 patients:

- Baseline BCVA (≥ 64 letters and ≤ 63 letters)
- Baseline DR severity (<47, ≥ 47- ≤ 53, > 53 ETDRS DRSS)
- Baseline HbA1c (≤ 8 %, > 8 %)
- Age (< 65 years, ≥ 65 years)
- Gender (Female and Male)

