average benefit of +3.6 letters (p=0.03; 80% CI: 1.5 to 5.6 letters) over anti-VEGF monotherapy (adjusted for baseline variables) at Week 24 (1 month after the last monthly dose administered at Week 20), which was statistically significant in a mixed-model repeated measures analysis. In this anti-VEGF treatment-naïve population, the mean change in BCVA from baseline in the 6-mg faricimab group and the 1.5-mg faricimab group at Week 24 was 13.9 letters and 11.7 letters, respectively, relative to 10.3 letters in the 0.3-mg ranibizumab group. The proportion of treatment-naïve patients gaining 15 letters or more from baseline over time at Week 24 was 35.3% for the 0.3-mg ranibizumab group relative to 36.0% and 42.5% for the 1.5-mg and 6-mg faricimab groups, respectively. In addition to DME benefit, higher rates of improvement in DR severity from baseline (as assessed on the ETDRS Diabetic Retinopathy Severity Scale [DRSS]) were also observed with faricimab compared with anti-VEGF monotherapy in the anti-VEGF treatment-naïve cohort, with 27.7% and 38.6% of patients (1.5-mg and 6-mg faricimab, respectively) experiencing a ≥ 2-step improvement from baseline to Week 24 compared with 12.2% in the 0.3-mg ranibizumab treatment cohort.

For the previously anti-VEGF–treated population, the absolute change from baseline was 9.6 letters and 8.3 letters for the 6-mg faricimab group and the anti-VEGF group, respectively. The difference of +1.3 letters was directionally similar to the treatment-naïve cohort but was not statistically significant (p=0.635; 80% CI: -2.3 to 5.0). Additionally, the proportion of patients gaining 15 or more letters from baseline over time at Week 24 was 23.2% and 16.8% for the 6-mg faricimab and anti-VEGF SOC treatment arms, respectively. The anatomical outcomes showed directionally similar benefits for faricimab in this cohort.

Overall, the data from the intent-to-treat study population (both treatment-naïve and previously anti-VEGF—treated patients) suggest consistent benefit and safety profile of faricimab over anti-VEGF monotherapy in the general DME population, with no new safety signals being observed.

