- 7. DME defined as macular thickening by spectral-domain optical coherence tomography (SD-OCT) involving the center of the macula: CST of ≥325 µm with Spectralis® (Heidelberg Engineering, Heidelberg, Germany) at screening. This inclusion criterion is to be assessed by the central reading center (CRC).
- 8. Decreased VA attributable primarily to DME, with BCVA letter score of 75 to 20 letters (both inclusive) on ETDRS-like charts at the screening visit
- Clear ocular media and adequate pupillary dilation to allow acquisition of good quality retinal images to confirm diagnosis

Contraception

- 10. For women of childbearing potential (WOCBP): agreement to remain abstinent (refrain from heterosexual intercourse) or use contraception as defined below:
 - Women must remain abstinent or use contraceptive methods with a failure rate of < 1% per year during the treatment period and for at least 3 months after the final dose of faricimab.
 - A woman is considered to be of childbearing potential if she is postmenarchal, has not reached a postmenopausal state (≥ 12 continuous months of amenorrhea with no identified cause other than menopause), and is not permanently infertile due to surgery (i.e., removal of ovaries, fallopian tubes, and/or uterus) or another cause as determined by the investigator (e.g., Müllerian agenesis). The definition of childbearing potential may be adapted for alignment with local guidelines or regulations.
 - Examples of contraceptive methods with a failure rate of < 1% per year include bilateral tubal ligation, male sterilization, hormonal contraceptives that inhibit ovulation, hormone-releasing intrauterine devices, and copper intrauterine devices.
 - Contraception methods that do not result in a failure rate of <1% per year such as male or female condom with or without spermicide; and cap, diaphragm, or sponge with spermicide are not acceptable.
 - The reliability of sexual abstinence should be evaluated in relation to the duration of the clinical study and the preferred and usual lifestyle of the patient. Periodic abstinence (e.g., calendar, ovulation, symptothermal, or postovulation methods) and withdrawal are not adequate methods of contraception. If required per local guidelines or regulations, locally recognized adequate methods of contraception and information about the reliability of abstinence will be described in the local ICF.

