Appendix 1: Schedule of Activities

- Both refraction and BCVA must be performed prior to pupil dilation (study eye and non-study eye), the faricimab IVT injection in the study eye and, if applicable, the anti-VEGF treatment in the non-study eye. Screening BCVA (not baseline) used for eligibility. Both refraction and BCVA will be assessed at every study visit (as indicated in the table above) for the study eye, but only at the screening visit, the baseline visit, and the SFV / ETV for the non-study eye (fellow eye).
- ^k Performed prior to the faricimab IVT injection (study eye) and, if applicable, the anti-VEGF treatment (non-study eye). All imaging procedures will be performed at every study visit (as indicated in the table above) for the study eye, but only at the screening visit, baseline visit, and the SFV/ETV for the non-study eye (fellow eye).
- If the study site has the capability and is certified to perform SS-OCT-A and SD-OCT-A, the study site must perform SS-OCT-A only. If the study site does not have the capability or certification to perform SS-OCT-A, then the study site must perform SD-OCT-A. The study site must always perform SD-OCT. If the study site additionally has the capability and certification to perform SS-OCT, the study site should also perform SS-OCT.
- m Performed prior to the faricimab IVT injection (study eye) and, if applicable, the anti-VEGF treatment (non-study eye). It will be performed at every study visit (as indicated in the table above) for the study eye and the non-study eye (fellow eye).
- The screening IOP, pretreatment IOP, and SFV or ETV IOP of the study eye and, if applicable, the non-study eye (fellow eye) should be performed prior to dilating the eyes. Post-treatment IOP measurement in the study eye and, if applicable, in the non-study eye (fellow eye) should be performed 30 (±15) minutes post-treatment (thus also after the AH tap [study eye only]) by qualified personnel. If there are no safety concerns after 30 (±15) minutes following the study treatment, the patient will be permitted to leave. If the IOP value is of concern to the Investigator, the patient will remain in the clinic and will be managed in accordance with the Investigator's clinical judgment. The adverse event will be recorded on the adverse event eCRF as applicable the clinic.

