2.2 OUTCOME MEASURES

2.2.1 Exploratory Endpoints

To explore the associations over time between clinical assessments, multimodal imaging assessments, AH biomarker patterns and genetic polymorphisms:

- Proportion of patients with a ≥2-step ETDRS DRSS improvement from baseline over time
- Proportion of patients with a ≥3-step ETDRS DRSS improvement from baseline over time
- Changes from baseline in BCVA (as measured on the ETDRS chart) over time
- Changes from baseline in IRF (intraretinal fluid) over time
- Changes from baseline in SRF (subretinal fluid) over time
- Changes from baseline in CST over time
- · Changes from baseline in multimodal imaging over time including:
 - Central retinal thickness
 - Foveal avascular zone (FAZ) / retinal nonperfusion
 - Vessel density
 - Periphery status (ischemia and proliferation)
 - Microaneurysm location, number, and turnover
 - Ischemic area
- Changes from baseline in AH biomarker patterns over time including:
 - Proteins, including but not limited to: cytokines, chemokines, and growth-, angiogenesis-, and complement-related factors, etc.
 - Metabolites, including but not limited to: lipids, sugars, amino acids, etc.
- Genetic polymorphisms via standard clinical genotyping
- Advanced analytics tools (e.g., artificial intelligence-based tools) for the assessment of clinically relevant features

2.2.2 Pharmacokinetic Endpoints

Not Applicable.

2.2.3 Safety Endpoints

The Safety endpoints are:

- Incidence and severity of adverse events
- Description of ocular assessments
- Study treatment exposure and Anti-VEGF exposure for fellow eye
- Laboratory assessments (only HbA1c assessments)
- Concomitant medication
- Concurrent ocular procedures

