4.3 DEMOGRAPHIC AND BASELINE CHARACTERISTICS

Baseline is defined as the last available measurement obtained on or prior to the day of first dose. Patients with missing baseline assessments will not be imputed.

The following demographic and baseline characteristics will be summarized for the mITT population:

- Age (years) as continuous variable and age in category < 65 years, ≥ 65 years
- Gender (Male and Female)
- Self-reported race and ethnicity
- Region
- Female reproductive status
- Smoking history (never, current, former)
- Diabetes mellitus (Type 1, Type 2)
- Baseline HbA1c as continuous and in category < 6.5 %, ≥ 6.5 < 8 % and ≥ 8%
- Systolic blood pressure (mmHg) as continuous variable and its category <140 mmHg, >=140 and <160 mmHg and >=160 mmHg
- Diastolic blood pressure (mmHg) as continuous variable
- Blood pressure (mmHg) in category (> 160 systolic or > 90 diastolic, <= 140 systolic and <= 85 diastolic and <= 120 systolic and <= 80 diastolic)

Baseline ocular characteristics:

- Baseline ocular characteristics description will be done in study eye and fellow eye (analyzed separately).
 - Study eye selection (Eligible eye (right, left, bilateral) and selected eye (right, left)).
 - Diabetic macular edema (Yes/No) (for fellow eye only)

- Diabetic macular edema status at baseline (Resolved/Ongoing) (for fellow eye only)
- Duration since Diabetic macular edema initial diagnosis Onset (in months) and its category (≤ 3 months and >3 months) (date of baseline visit – onset date of Diabetic macular edema diagnosis +1) / 30.4375.
- Baseline BCVA
- Baseline ocular assessments
 - Center subfield thickness (CST)
 - Macular Ischemic Non-Perfusion (Yes/No): Absence is defined as Total area of capillary non perfusion within the macula of 0 to 0.1 mm2.
 - Macular leakage (Yes/No): Absence is defined as Total area of fluorescein leakage within the macula of 0 mm2
 - Intraocular Pressure (mmHg)
 - Lens status (phakic, pseudophakic, aphakic, other)
 - Global Diabetic retinopathy status (ETDRS scale into 12 step) from Ultra-widefield Fundus Photography (UWF-C)
 - Diabetic retinopathy status (ETDRS scale into 12 step) from Color Fundus Photography (FP-7M

A listing of Demographics and relevant baseline characteristics will be presented.

General medical history and baseline conditions:

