- i. Both refraction and BCVA must be performed prior to pupil dilation (study eye and non-study eye), the faricimab IVT injection in the study eye and, if applicable, the anti-VEGF treatment in the non-study eye. Screening BCVA (not baseline) used for eligibility. Both refraction and BCVA will be assessed at every study visit (as indicated in the table above) for the study eye, but only at the screening visit, the baseline visit, and the SFV / ETV for the non-study eye (fellow eye).
- j. Performed prior to the faricimab IVT injection (study eye) and, if applicable, the anti-VEGF treatment (non-study eye). All imaging procedures will be performed at every study visit (as indicated in the table above) for the study eye, but only at the baseline visit and the SFV / ETV for the non-study eye (fellow eye).
- k. If the study site has the capability to perform SS-OCT-A and SD-OCT-A, the study site must perform SS-OCT-A only. If the study site does not have the capability to perform SS-OCT-A, then the study site must perform SD-OCT-A. Similarly, if the study site has the capability to perform SS-OCT and SD-OCT, the study site must perform SS-OCT only. If the study site does not have the capability to perform SS-OCT, then the

- study site must perform SD-OCT.
- I. The finger-counting test should be conducted within approximately 15 minutes of study treatment administration for the study eye and, if applicable, the non-study eye (fellow eye).
- m. The screening IOP, pretreatment IOP, and SFV or ETV IOP of the study eye and, if applicable, the non-study eye (fellow eye) should be performed prior to dilating the eyes. Post-treatment IOP measurement in the study eye and, if applicable, in the non-study eye (fellow eye) should be performed 30 (±15) post-treatment (thus also after the AH tap [study eye only]) by qualified personnel. If there are no safety concerns after 30 (±15) minutes following the study treatment, the patient will be permitted to leave. If the IOP value is of concern to the investigator, the patient will remain in the clinic and will be managed in accordance with the investigator's clinical judgment. The AE will be recorded on the AE eCRF as applicable the clinic.
- n. May only be performed after the AH tap (study eye only) and if patient is a WOCBP their pregnancy test (urine) must be negative. Only the study eye will receive the faricimab IVT injection.

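### The SAP sorts eyes into BCVA subgroups on the same Day 1 score that is subtracted in BCVA change, so regression to the mean alone makes the low-vision subgroup appear to gain more

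*SAP*

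**What the plan says.** SAP 4.4.3 sets the rule: "The exploratory endpoints will be summarized by the following subgroups, provided that they include at least 30 patients". The first subgroup factor listed is "Baseline BCVA (≥ 64 letters and ≤ 63 letters".

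SAP 4.3 gives the only definition of baseline: "Baseline is defined as the last available measurement obtained on or prior to the day of first dose". BCVA is scheduled at screening and again on Day 1, before the injection: "Both refraction and BCVA will be assessed at every study visit (as indicated in the table above) for the study eye" (Protocol Appendix 1). Baseline BCVA is therefore the Day 1 score, or the screening score if Day 1 is missing.

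The affected endpoint is "Changes from baseline in BCVA (as measured on the ETDRS chart) over time" (SAP 2.2.1). SAP 4.4.1.1 analyses it with an MMRM that has baseline BCVA, age and region as covariates. No subgroup version of that model is given, and SAP 4.4.2 plans no sensitivity analysis.

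Eligibility rests on the other pre-treatment score, a "BCVA letter score of 75 to 20 letters (both inclusive) on ETDRS-like charts at the screening visit" (Protocol 4.1.1). SAP Appendix 2 confirms it: "Screening BCVA (not baseline) used for eligibility". Every enrolled patient should therefore have a screening BCVA.

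**The concern.** One measurement does two jobs. It decides which subgroup an eye joins, and it enters the outcome with a minus sign. Its test error is then shared by grouping and outcome. The ≤63-letter group collects eyes whose Day 1 score was too low by chance, and they drift back up. The ≥64-letter group collects eyes whose score was too high, and they drift down. A difference in mean gain appears even if treatment acts identically on all eyes.

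Nothing in the plan would expose this. The study has one arm, so no untreated subgroup shows the same drift. The direction, with worse eyes gaining more, is also clinically plausible, so a reader would have little reason to suspect an artefact. In a study meant to generate hypotheses, a built-in signal about starting vision could be carried into later work.

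**Working it through.** **The plan's own figure.** There is none. The documents give no BCVA SD, no test–retest error and no allowance for regression to the mean. The only design calculation concerns a correlation and does not bear on this point.

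**Inputs from the documents.** Cut at 63/64 letters (SAP 4.4.3); screening eligibility 20–75 letters (Protocol 4.1.1); screening 1 to 28 days before Day 1 (Protocol Appendix 1); up to 99 patients (SAP 2.3).

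**Assumed inputs.** Each score is a stable true value plus visit error. The reference population has true BCVA with mean 62 and SD 12 before the eligibility cut. Error SD is 2 to 6 letters per visit. Screening and Day 1 errors correlate at ρ = 0, 0.25 or 0.5. The true gain is the same in every eye.

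**Step 1: the mechanism.** Let Day 1 = T + e1 and follow-up = T + g + e2. Then change = g + e2 − e1. With g constant and e2 independent of the grouping:

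mean gain (low) − mean gain (high) = mean e1 (high) − mean e1 (low).

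This is positive whenever the grouping is made on T + e1.

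**Step 2: size by hand.** The difference is roughly (1 − reliability) × (gap between the subgroups' Day 1 means). For a normal variable split near its middle, the gap is about 1.596 SD. Since 1 − reliability is about error variance / SD², the difference is about 1.596 × error variance / SD, where SD is that of Day 1 BCVA among enrolled eyes:

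- error SD 2: 1.596 × 4 / 10.01 = 0.64
- error SD 3: 1.596 × 9 / 10.30 = 1.39
- error SD 4: 1.596 × 16 / 10.68 = 2.39
- error SD 5: 1.596 × 25 / 11.14 = 3.58

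**Step 3: simulation with the eligibility rule applied.** Entries are the spurious low-minus-high difference in gain, in letters. Brackets give the Day 1 cut at the same ρ.

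| Error SD | Day 1 cut, ρ = 0 | Screening cut, ρ = 0 | Screening cut, ρ = 0.25 | Screening cut, ρ = 0.5 |
|---|---|---|---|---|
| 2 | 0.66 | 0.0 | 0.11 (0.60) | 0.21 (0.55) |
| 3 | 1.46 | 0.0 | 0.23 (1.33) | 0.47 (1.20) |
| 4 | 2.51 | 0.0 | 0.39 (2.29) | 0.80 (2.07) |
| 5 | 3.74 | 0.0 | 0.60 (3.49) | 1.19 (3.15) |
| 6 | 5.1 | 0.0 | about 0.9 | about 1.7 |

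The hand figures agree with the second column. A narrower true spread gives somewhat more: for mean 64 and SD 8 the Day 1 cut gives 4.62 letters at error SD 5, and about 6.2 at error SD 6.

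**Step 4: what the screening cut leaves.** With independent errors the screening label carries no information about e1, so nothing remains. The 20–75 eligibility rule does not bring the artefact back, because that regression happens between screening and Day 1, before the change score starts. With correlated errors the label carries part of e1. At error SD 5 the remainder is 0.60 / 3.49 = 17% at ρ = 0.25 and 1.19 / 3.15 = 38% at ρ = 0.5. Measured against the independent-error artefact, the first is 0.60 / 3.74 = 16%. In the narrowest population it reaches 1.79 / 4.18 = 43%.

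**Step 5: price of the screening cut.** With independent errors, about 8% (error SD 2) to 24% (error SD 6) of eyes fall on different sides of 63/64 at the two visits. That is 0.08 × 99 ≈ 8 to 0.24 × 99 ≈ 24 patients.

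**The case against.** **The output is descriptive.** SAP 4.4.3 only summarises; it specifies no subgroup test, interaction or decision. This stands, and it limits the weight of the point. A reader might infer that the subgroups are there to identify responders, but the SAP does not say so.

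**The MMRM already adjusts for baseline BCVA.** No subgroup model is specified. If the model were fitted within each subgroup, each adjusted mean would sit at that subgroup's own baseline mean and keep the artefact. One pooled model with baseline BCVA and a subgroup term would leave only about 0.0–0.5 letters at error SDs of 3–6. But it would also absorb a genuine linear dependence of gain on starting vision, so it answers a different question.

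**The size is assumed.** This also stands. Examiners and rooms are certified (Protocol Appendix 4), so the low end, under 1 letter at error SD 2, cannot be dismissed.

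**Screening is not a clean substitute.** Screening may fall the day before Day 1, so shared fluctuation is plausible. It is tempting to say that the screening cut removes the artefact outright; that holds only for independent errors. Nor is the relabelling confined to a handful of patients: the assumptions that make the artefact large also make the relabelling large.

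**A benchmark to avoid.** A reader might set the artefact beside the faricimab–ranibizumab difference in Protocol 1.3.2, an "average benefit of +3.6 letters". That figure is a baseline-adjusted contrast between randomised arms of another trial. It is not a yardstick for an unadjusted contrast between subgroups of one arm.

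**Conclusion.** The coupling follows directly from SAP 4.3, 4.4.3 and 4.4.1.1 and needs no assumption beyond some test error on Day 1. Its direction is certain: it favours the ≤63-letter subgroup. Its size is not known from the documents. In the reference population it is roughly 0.7–5 letters for assumed error SDs of 2–6. Grouping on screening BCVA removes it under independent errors and otherwise leaves about 16–40% at error correlations of 0.25–0.5.

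The finding covers BCVA change by BCVA subgroup only. CST, fluid and angiographic endpoints do not share this measurement with the BCVA grouping. The DR-severity subgroups may have the same weakness for DRSS step change, but that was not quantified, and SAP 4.4.3 does not say whether the ultra-widefield or the 7-field grading defines them. A real or ceiling-related difference by starting vision would remain after the change, as it should. The amendment is worth making, though it affects one descriptive table rather than the study's main results.

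**What to change.** Add to SAP 4.4.3: *For change from baseline in BCVA, the BCVA subgroup is assigned from the study-eye BCVA of the screening visit that led to enrolment; change is still measured from Day 1.* Keep the 63/64 cut. Naming that screening visit settles which score applies to re-screened patients.

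Three details complete it:

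- Keep the Day 1-defined summary as a supplementary table, with a note that it includes regression to the mean.
- Flag and count patients whose baseline falls back to screening because Day 1 BCVA is missing. For them one score again does both jobs.
- Apply the 30-patient minimum to the screening-defined groups.

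The cost is one sentence, one extra table and a footnote; no new data are needed. The statistical price is that about 8–24% of patients carry a label that differs from their Day 1 score. This slightly dilutes any real subgroup difference but does not create one.

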4.5 PHARMACOKINETIC AND PHARMACODYNAMIC ANALYSES

No pharmacokinetic or pharmacodynamic analyses are planned in this study.

4.6 SAFETY ANALYSES

Safety analyses will be based on the Safety-evaluable population.

Safety will be assessed through descriptive summary of ocular and non-ocular adverse events, deaths, and ocular assessments (e.g., IOP, slit lamp and indirect ophthalmoscopy). Clinically significant laboratory abnormalities and clinically significant vital sign abnormalities will be reported as adverse events and evaluated as part of the adverse event assessments.

4.6.1 Exposure of Study Treatment

Study treatment exposure (treatment duration and number of study drug administrations) will be summarized with descriptive statistics.

For the Fellow eye, the anti-VEGF treatment duration, number of administrations and the conditions/diagnosis for which the treatment was given will be described.

